### **Post-treatment Follow-up Visits**

In-person follow-up interviews and assessments will be conducted with each Veteran participant. Follow-up will occur 1 to 2 weeks after the final therapy session (for completers) or 11 to 12 weeks after baseline (for those who drop out) to assess changes in PTSD, perceptions of moral injury, anger, aggression, trauma-related guilt, depression, substance use, and suicide-related constructs. For those randomized to TAU, follow-up will occur 11 to 12 weeks after

baseline. The CAPS and all baseline assessments will be re-administered. The CAPS will not be administered by any of the study therapists. To assess the degree to which participants trusted and felt respected and understood by the therapist, the *Helping Alliance Questionnaire* (Luborsky *et al.*, 1996) will also be administered at the follow-up visit.

Qualitative interviews following an interview guide will be administered to all participants. For those completed treatment, questions will evaluate treatment acceptability, as well as participants' impressions of whether and how the therapy was (or was not) helpful to them. For those who dropped out, reasons for dropout at each treatment phase will be explored. The qualitative portion of the post-treatment follow-up visit will be audio recorded using the Olympus DM-720 4GB Digital Voice Recorder or the Olympus DM-620, which are newer models of the approved-for-use Olympus DM-420. Recordings will be transcribed and analyzed using thematic analysis.

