## Specific Aims

The overall objective of this application is to gather data on the feasibility and acceptability of Narrative Exposure Therapy (NET) in a pilot sample of Veterans with PTSD and history of anger and aggression. We are also interested in evaluating whether the intervention has the potential to have an effect on key clinical outcomes, including PTSD symptoms, suicidality, substance abuse, and aggression.

The following **Specific Aims** have been developed for this project:

**Aim 1:** Evaluate study feasibility and treatment delivery procedures of Narrative Exposure Therapy (NET) in Veterans with PTSD and history of anger and aggression. Data gathered will include recruitment rates, drop-out rates, adverse event frequency and severity, participant engagement in treatment, and therapist fidelity.

**Aim 2:** Collect data on appropriateness of assessment measures of key clinical constructs in the Veteran population. Clinical outcomes evaluated will include PTSD symptoms, suicidality, substance abuse, and aggression.

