### Evaluation of Specific Aims

**Specific Aim 1.** *Evaluate study feasibility and treatment delivery procedures of Narrative Exposure Therapy (NET) in with a history of aggression and PTSD. Data gathered will include recruitment rates, drop-out rates, adverse event frequency and severity, participant engagement in treatment, and therapist fidelity.*

To evaluate recruitment rates, we will track the number of Veterans who complete the in-person screening.. To evaluate retention rates, we will consider retention rates > 80% to be successful. Retention will be defined as completing at least 7 of 10 sessions, with the last sessions being a mutually-agreed upon final session. Retention strategies will include: 1) reminder calls, texts, and/or emails 24 hours prior to each study visit; 2) asking each participant at the end of each session about his or her intent to attend the next session; and 3) small appreciation gifts (e.g., pens, magnetized note pads, and thermoses). The second technique has been used successfully in previous clinical trials, and also provides information for assessing the assumption of ignorable attrition required for mixed effects analyses (Leon, Demirtas, & Hedeker, 2007). The third technique has proven extremely helpful in recent longitudinal studies, resulting in high retention rates (Elliott et al., 2015; Cook et al., 2015; Kimbrel, Meyer et al., manuscript in preparation; Kimbrel, Flynn et al., 2015). For those participants who drop out of treatment, we will 1) attempt to contact them to offer compensation for participation in the qualitative interview regarding their reasons for withdrawal and in the post-treatment assessments; and 2) encourage them to complete subsequent study assessments. Qualitative interviews will be audio recorded, and analyses will help identify ways that the intervention can be further tailored to reduce dropout and to meet the needs of justice-involved Veterans.

To facilitate therapist fidelity, consultation will be provided via telephone or video conferencing by national expert on NET, [name], and/or by one of the developers of the NET adaptation for traumas involving harm to others, [name]. Study therapists will evaluate treatment fidelity after every session using checklists specifically

developed for NET. This checklist will be adapted to maximize effectiveness in future trials over the course of this pilot.

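### The direct acceptability questions are assigned to Veterans who completed treatment, so the acceptability findings would be conditional on completion

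*Protocol*

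**What the plan says.** The protocol's Specific Aims section gives the overall objective as to "gather data on the feasibility and acceptability of Narrative Exposure Therapy (NET) in a pilot sample of Veterans". Acceptability does not reappear in the data listed for Aim 1: "Data gathered will include recruitment rates, drop-out rates, adverse event frequency and severity, participant engagement in treatment, and therapist fidelity".

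The section Post-treatment Follow-up Visits plans an interview for everyone: "Qualitative interviews following an interview guide will be administered to all participants". Its content then depends on treatment status. On one side, "For those completed treatment, questions will evaluate treatment acceptability", together with the participant's view of whether and how the therapy helped. On the other, "For those who dropped out, reasons for dropout at each treatment phase will be explored". The recordings are to be transcribed and analysed by theme.

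Under Evaluation of Specific Aims, the text for Aim 1 describes the drop-out interview in the same way. Staff will "attempt to contact them to offer compensation for participation in the qualitative interview regarding their reasons for withdrawal and in the post-treatment assessments".

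The Helping Alliance Questionnaire "will also be administered at the follow-up visit", with no restriction to completers. The measures table under Three-month Follow-up contains no acceptability or satisfaction scale.

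**The concern.** Whether a Veteran finishes a demanding exposure therapy depends in part on whether he or she finds it acceptable. If the direct questions go to those who finished, the answers come from a group selected partly on the thing being asked about. The Veterans most likely to have reservations about the therapy would then give their reasons for leaving but no direct view of its acceptability or of whether the sessions they attended helped.

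This is a matter of data collection. If the questions are not put to drop-outs, no later analysis plan can recover the answers. It bears on a named part of the objective. It also bears on the stated use of the interviews under Aim 1, which is to learn how to adapt the therapy so that fewer people leave. That comparison is clearest when both groups have answered the same questions.

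**Working it through.** **Where the protocol could capture acceptability**

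- *Completers' interview* (Post-treatment Follow-up Visits): direct questions on acceptability and helpfulness.
- *Drop-outs' interview* (same section, and Aim 1 under Evaluation of Specific Aims): reasons for leaving, by treatment phase. This is relevant but indirect. The protocol itself mentions a large catchment area and possible full days off work (Protections Related to Undue Influence), so a Veteran may leave for practical reasons while finding NET acceptable, or may leave because the narration was too distressing. A direct question helps to separate the two.
- *Helping Alliance Questionnaire*: open to all who attend follow-up, but it concerns the relationship with the therapist.
- *Drop-out rates, engagement and intent to attend the next session* (Aim 1): not limited to completers. They record behaviour and intention, not the participant's view of the treatment.

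The only direct acceptability questions described are therefore those assigned to completers.

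**Who counts as a completer.** The interview text does not define completion. Aim 1 defines retention as seven or more of the ten sessions, with the last one agreed to be final. If that rule applies, a Veteran who stopped after six sessions falls on the drop-out side. The protocol does not say whether it applies.

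**Size.** The protocol gives no acceptability figure to reproduce. Its one related sample figure does reproduce: 20 / 0.70 = 28.57, rounded up to the stated 29 baseline assessments.

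Let c be the share of NET starters who complete, and pc and pd the shares of completers and drop-outs who find NET acceptable.

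- All starters: c × pc + (1 - c) × pd
- Completers only: pc
- Overstatement: pc - [c × pc + (1 - c) × pd] = (1 - c)(pc - pd)

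Inputs: the final sample is 20 (Participants) and the retention benchmark is above 80% (Aim 1). The smallest count of 20 above the benchmark is 17, since 16/20 is exactly 80%. The values pc = 90% and pd = 0 to 90% are assumptions. Overstatement in percentage points:

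| Completing | pd = 0 | pd = 25% | pd = 50% | pd = 90% |
|---|---|---|---|---|
| 17/20 (c = 0.85) | 13.5 | 9.75 | 6 | 0 |
| 16/20 (c = 0.80) | 18 | 13 | 8 | 0 |
| 14/20 (c = 0.70) | 27 | 19.5 | 12 | 0 |

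Example: at c = 0.80 and pd = 25%, all starters = 0.80 × 90% + 0.20 × 25% = 77%, against 90% in completers, a gap of 13 points. If pd were 100%, all starters would be 92% and the completers' figure would be 2 points too low.

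The number starting NET is uncertain. Overview of Study Visits says eligible Veterans are assigned to NET, while other sections refer to participants randomised to TAU. With an assumed 1:1 split, 10 would start NET. The formula uses only shares, so 8/10 gives the same result as 16/20.

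**The case against.** The best defence is that drop-outs are not ignored. Everyone is to be interviewed, drop-outs are asked phase by phase why they left, and compensation is offered for that interview and for the assessments. Reasons for leaving are evidence of what was not acceptable. The alliance questionnaire, the drop-out rate against a benchmark and the session-by-session intent question also cover Veterans who later leave. Completers are invited to say that the therapy did not help. Tailoring a small qualitative interview to treatment status is a defensible choice, and the protocol only summarises a guide that is not shown, so some overlap in questions cannot be ruled out.

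Much of this stands, and it limits the point. A reader might infer that drop-outs' unfavourable views will be lost, that the trial will present completers' views as those of all Veterans treated, or that acceptability will be inflated by a known number of points. The documents support none of these. Unfavourable evidence is sought in another form. Nothing says that completer themes will be generalised or drop-out themes left out. The planned output is thematic, with no acceptability rate, threshold or decision rule to inflate.

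What the defence does not supply is a direct acceptability or helpfulness question for Veterans who started NET and left. The text on Aim 1 again confines their interview to withdrawal: "participation in the qualitative interview regarding their reasons for withdrawal".

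**Conclusion.** The point holds as a modest and inexpensive improvement. As written, the protocol's direct acceptability findings are conditional on completing treatment, and they are likely to lean favourable. That direction is a judgement: it requires drop-outs to view NET less favourably than completers, which is plausible but not stated. The size is unknown. If someone summarised the completers' answers as a proportion, the overstatement for all starters would be (1 - c)(pc - pd), and at most (1 - c) × pc. With an assumed pc of 90%, that ceiling is 13.5 points at 17/20 completing, 18 at 80% and 27 at 70%. It is zero if the two groups agree. These figures illustrate the mechanism and do not estimate a bias in this trial.

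**What to change.** In Post-treatment Follow-up Visits and in the interview guide:

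- Put one common core to every participant who attended at least one NET session: acceptability, whether and how the sessions attended helped, and reasons to continue or to stop. This also makes the undefined boundary of completion unimportant for deciding who is asked.
- Keep the phase-specific dropout questions as an add-on.
- Report themes for all treated participants, with completers and drop-outs side by side and the number interviewed in each group.
- Align the Aim 1 text, which now describes the drop-out interview as being about withdrawal.

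If the split is kept, label the acceptability result as applying to completers only.

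The cost is wording, since the interviews, recording, transcription and offer of compensation are already planned. Drop-out interviews become slightly longer, and the reported acceptability may be less favourable.

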### **Three-month Follow-up**

Three months after the final treatment session, packets of questionnaires including the baseline measures will be mailed along with a self-addressed, stamped return envelope, to participants regardless of drop-out status.

Measure	Screening	Baseline	Post-treatment	3 months
Demographics Questionnaire	X			
The Traumatic Life Events Questionnaire	X			
The Clinician-Administered PTSD Scale	X		X	
The Structured Clinical Interview for DSM-V (Psychosis, Substance Misuse Modules)	X			
The Appetitive Aggression Scale		X	X	
The Killing Cognitions Scale*		X	X	
PTSD Checklist for the DSM-5 (PCL-5)**		X	X	X
The Moral Injury Events Scale		X	X	X
Revised Conflict Tactics Scales		X	X	X
Dimensions of Anger Reactions		X	X	X
Trauma-Related Guilt Index		X	X	X
Beck Depression Inventory		X	X	X

Acquired Capability for Suicide Scale - Fearlessness About Death		X	X	X
Depressive Symptom Index: Suicidality Subscale		X	X	X
Interpersonal Needs Questionnaire		X	X	X
The Alcohol Use Disorder Identification Test		X	X	X
The Drug Abuse Screening Test		X	X	X
The Helping Alliance Questionnaire			X	

\* The Killing Cognitions Scale will only be administered if participants endorse having killed in the context of war on Part 1 of the Appetitive Aggression Scale.

\*\* To evaluate the change in PTSD symptoms over time, participants will be administered the PCL-5 at each session.

### Evaluation of Specific Aims

**Specific Aim 1.** *Evaluate study feasibility and treatment delivery procedures of Narrative Exposure Therapy (NET) in with a history of aggression and PTSD. Data gathered will include recruitment rates, drop-out rates, adverse event frequency and severity, participant engagement in treatment, and therapist fidelity.*

To evaluate recruitment rates, we will track the number of Veterans who complete the in-person screening.. To evaluate retention rates, we will consider retention rates > 80% to be successful. Retention will be defined as completing at least 7 of 10 sessions, with the last sessions being a mutually-agreed upon final session. Retention strategies will include: 1) reminder calls, texts, and/or emails 24 hours prior to each study visit; 2) asking each participant at the end of each session about his or her intent to attend the next session; and 3) small appreciation gifts (e.g., pens, magnetized note pads, and thermoses). The second technique has been used successfully in previous clinical trials, and also provides information for assessing the assumption of ignorable attrition required for mixed effects analyses (Leon, Demirtas, & Hedeker, 2007). The third technique has proven extremely helpful in recent longitudinal studies, resulting in high retention rates (Elliott et al., 2015; Cook et al., 2015; Kimbrel, Meyer et al., manuscript in preparation; Kimbrel, Flynn et al., 2015). For those participants who drop out of treatment, we will 1) attempt to contact them to offer compensation for participation in the qualitative interview regarding their reasons for withdrawal and in the post-treatment assessments; and 2) encourage them to complete subsequent study assessments. Qualitative interviews will be audio recorded, and analyses will help identify ways that the intervention can be further tailored to reduce dropout and to meet the needs of justice-involved Veterans.

To facilitate therapist fidelity, consultation will be provided via telephone or video conferencing by national expert on NET, [name], and/or by one of the developers of the NET adaptation for traumas involving harm to others, [name]. Study therapists will evaluate treatment fidelity after every session using checklists specifically

developed for NET. This checklist will be adapted to maximize effectiveness in future trials over the course of this pilot.

To evaluate participant retention through the 3 month assessment, we will consider the larger RCT feasible if 70% of Veterans complete the 3 month assessment. As recommended by Wisniewski and colleagues (Wisniewski, Leon, Otto, & Trivedi, 2006), we will maintain frequent participant contact throughout the evaluation period. For example, we will make intermittent phone calls to participants to check on their status, and send birthday and holiday cards to encourage a sense of community and ownership of the study.

Adverse event monitoring is discussed in detail in the Human Subjects section of this proposal. Though we do not anticipate adverse events to be frequent or severe, if we observe a problem with adverse events we will build precautions into the structure of the treatment protocol and the study design.

***Specific Aim 2. Collect data on appropriateness of assessment measures for measuring key clinical constructs in Veterans with a history of aggression. Clinical outcomes evaluated will include PTSD symptoms, suicidality, substance abuse, and aggression.***

Change scores from baseline to 3 months post-baseline on the CAPS and on measures of PTSD symptom severity, perceptions of moral injury, anger, aggression, trauma-related guilt, depression, substance use, and suicide-related constructs will be calculated using the measures listed in the baseline section above. Measures will be evaluated for acceptable variability, and for absence of floor or ceiling effects in this sample.

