## Methods

### Overview of Study Visits

This pilot feasibility trial will use a randomized controlled design to 1) evaluate and refine the treatment access and delivery procedures in a Veteran sample; 2) evaluate and develop procedures to ensure therapist fidelity; 3) evaluate the adequacy of outcome measures (i.e. distribution of scores, potential ceiling or floor effects); and 4) identify potential reasons for treatment adherence and treatment dropout.

Participants will be screened over the phone to determine whether basic inclusion criteria are met, after which they will be invited to an in-person screening visit at the laboratory. At the laboratory screening and baseline visit, informed consent will be obtained. Veterans who meet inclusion criteria will be assigned to NET.

Study participation will include a baseline visit, participation in 10 weekly therapy sessions if randomized to NET a post-treatment follow-up visit, and completion of 3-month follow-up questionnaires by mail.

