## Study Visits

Three licensed clinical psychologists who have been trained by some of the original developers in Narrative Exposure Therapy will provide therapy in this study. As needed, consultation will be provided via telephone or video conferencing by national expert on NET, [name]., and/or by one of the developers of FORNET, [name].

Participants will attend 10 weekly study visits of 90 minutes each. Session one will involve a psychoeducation session wherein the symptoms and etiology of PTSD are explained, and the rationale for treatment is provided. Session two will include development of the lifeline, during which the participant provides an overview of their life using a rope or string as symbol of the passage of time. The participant places flowers along the rope to symbolize positive events or relationships, and stones to symbolize negative events or traumas. A key element of VETNET is that the therapist will elicit discussion of what are often life-altering military-related events including military training, deployments, and separation from the military.

While creating the lifeline, participants will be offered the option to use sticks to symbolize events where they harmed another person. If participants do not indicate that they have ever harmed another person, then the adapted NET protocol will be used, though the possibility of using FORNET adaptations will be kept open if disclosure of harm is made later on in therapy. If participants do choose to use sticks in their lifeline, then the therapist will be alert to the possibility of needing to address moral injury or appetitive aggression by using adaptations specific to the FORNET protocol. In sessions three through nine participants will narrate key

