events in their lives, with specific focus on traumatic events as well as events when they harmed another person. During traumatic event narration, therapists will guide participants through slowly explaining the details of the event to allow for exposure and processing of previously avoided emotions, sensations, and thoughts. Therapists will encourage participants to stay in the trauma memory until anxiety, or other strong emotion, has peaked and has begun to subside. During narration of perpetration events, therapists will use a similar protocol, and will focus on contextualizing the perpetration event and contrasting the memory feelings (what was experienced at the time of the event) with the participant's feelings in the here and now while recalling the event. After each session, the therapist will create the written version of the narrative, and this will be read to the participant at the beginning of the following session. After the participant has made corrections or additions to the narrative, the process will proceed to the next critical event.

For all Veterans, whether the NET or FORNET protocol is used, therapists will include in the final session a component that will be unique to VETNET and that draws upon elements of Acceptance and Commitment Therapy (Hayes, 2004) and Adaptive Disclosure Therapy (Litz et al, 2009). This session will include an invitation to Veterans to consider how they will reconnect with their communities in ways that will build upon their strengths. The therapist will work with Veterans to identify their values, and how they would best act upon these to contribute in meaningful ways to their communities. Examples could be working at an animal shelter, volunteering at a church, joining a Veterans' service organization, or volunteering for a community garden, homeless shelter, or Habitat for Humanity. The therapist will help Veterans identify clear behavioral goals for following through on these ideas. The end of the final session will also include an evaluation and referral to services the Veteran is eligible for either within the VA or in the community such as housing assistance, educational assistance, or employment training, to continue to support successful reintegration.

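### Aim 1 fidelity is self-rated on a checklist that will change during the pilot, with no item set held constant and no statement that the VETNET and FORNET elements are rated

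*Protocol*

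**What the plan says.** Specific Aims and Evaluation of Specific Aims (both in the Protocol) list fidelity among the Aim 1 data: "Data gathered will include recruitment rates, drop-out rates, adverse event frequency and severity, participant engagement in treatment, and therapist fidelity". The method is given later under Aim 1. The therapists themselves complete the rating at the end of each session, on checklists made for NET, and the plan for the instrument is: "This checklist will be adapted to maximize effectiveness in future trials over the course of this pilot". The same paragraph provides for consultation by a NET expert and/or a developer of the adaptation for traumas involving harm to others.

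Overview of Study Visits gives fidelity a double purpose in this pilot: "evaluate and develop procedures to ensure therapist fidelity".

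The therapy delivered is wider than standard NET. Study Visits says of the lifeline session: "A key element of VETNET is that the therapist will elicit discussion of what are often life-altering military-related events". Of the last session it says that, for all Veterans, "therapists will include in the final session a component that will be unique to VETNET". FORNET adaptations come into play when a participant marks, or later discloses, having harmed another person. Otherwise the adapted NET protocol is used.

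**The concern.** One checklist has two jobs. It is a product the pilot is meant to improve, and it is the instrument that yields an Aim 1 result. If the scored items change part-way, a difference between early and late participants may reflect delivery, the items, or both, and the ratings alone cannot separate these.

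Coverage is a second matter. What is new here is the military content of the lifeline, the closing VETNET component, and the handling of perpetration events. If the checklist scores only standard NET steps, a high fidelity figure would say little about whether the adaptation was delivered as intended. A larger trial would need that information most.

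**Working it through.** The protocol gives no fidelity score, threshold or planned fidelity analysis, so there is no figure of its own to reproduce. The check sets the relevant sections side by side and then sizes the data involved.

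**1. Is the instrument fixed?** Evaluation of Specific Aims says it will be adapted during the pilot. No section lists the items, fixes a version for scoring, requires versions to be recorded, or says how ratings from different versions will be combined. Comparability over time is therefore not secured. Items left unchanged would stay comparable, but nothing says which items these are.

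**2. Are the added elements rated?**

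| Element delivered | Where described | For whom | Stated to be rated? |
|---|---|---|---|
| Military events in the lifeline | Study Visits, session two | All in therapy | No |
| VETNET final-session component | Study Visits, final session | All in therapy | No |
| FORNET adaptations for perpetration events | Study Visits, mainly sessions three to nine | Only if harm is indicated or disclosed | No |

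The checklist sentence names only NET. The sentence just before the checklist sentence distinguishes NET from its adaptation for harm to others. The final-session component is introduced as specific to VETNET, which the protocol itself proposes, so a checklist already developed for NET would not be expected to contain it. This shows that coverage is unstated. It does not show that coverage is absent.

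**3. Can early sessions be re-scored later?** Ratings are made by the therapist after each session. The only recordings described are of the qualitative interviews (Post-treatment Follow-up Visits; Privacy, Confidentiality and Information Security, data location). The therapist's written narrative would show which events were covered, but not how the session was conducted, and it is not listed among the stored study data. Re-scoring on a later checklist version is therefore not provided for.

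**4. How many ratings?** Inputs are 20 participants (Participants) and 10 sessions each (Study Visits).

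- All 20 receive NET: 20 × 10 = 200 ratings at most.
- Study Visits and Post-treatment Follow-up Visits also describe participants randomized to TAU, with no allocation ratio stated. Assuming 1:1, 10 × 10 = 100 at most.
- Each VETNET element belongs to one session per participant (session two or the final session), so each can be rated at most 20 times, or 10 times under the assumed split.
- Sessions three to nine give at most 20 × 7 = 140 ratings, or 10 × 7 = 70. FORNET items would apply to an unknown share of these.

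All are ceilings, because dropout and missed sessions lower them. They size the data and do not measure a bias.

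**The case against.** The strongest reply is that adaptation is intended. The stated pilot purpose joins evaluating and developing fidelity procedures, and the checklist is to be improved for future trials. No fidelity threshold, trend test or go/no-go rule is set, unlike session retention (above 80%) and the 3-month assessment (70%). Item content and version control often sit in a fidelity manual. Much of this stands: adapting the checklist is not an error, and no decision rule is corrupted. But the stated purpose includes evaluation, and that needs some items held constant. A later analysis document could not supply this, because the form must be settled before the first session.

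A reader might also draw stronger conclusions that the protocol does not support:

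- **That the checklist misses the new components.** No items are shown, the protocol often uses NET as the name for the whole intervention, and the planned adaptation may be the route by which VETNET items are added. The text is silent on coverage.
- **That early and late scores are not comparable.** This depends on which items change. The supportable statement is that comparability cannot be assumed.
- **That therapists alter the tool by which they are rated.** Self-rating is stated, but nobody is named as adapting the checklist.
- **That 200 ratings lack any common scale.** The figure ignores TAU participants, and unchanged items would remain common.
- **That FORNET content goes unscored throughout sessions three to nine.** Those adaptations are conditional. Since a history of physical aggression is an entry criterion, they may well be frequent, but the protocol gives no rate.

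**Conclusion.** The point holds in limited form. Fidelity is a promised, descriptive Aim 1 result, obtained by therapist self-rating on an instrument that will change while data accrue. The protocol neither holds an item set constant nor states that the VETNET and conditional FORNET elements are rated. As written, early and late ratings cannot be assumed comparable, and early sessions could not be re-scored later.

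The harm is confined to how the Aim 1 fidelity figure can be interpreted. The conclusion assumes that scored items may change, and that no therapy-session recordings exist beyond those described. It does not depend on the number of ratings. It is worth correcting because the remedy is cheap and leaves the development purpose intact.

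**What to change.** Before the first session, set a short core item set and leave it unchanged throughout. It should cover:

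- the NET steps: psychoeducation, lifeline, slowed narration of traumatic events, and reading back the narrative;
- the VETNET elements: military events in the lifeline, and the added final-session component;
- perpetration (FORNET) items, scored as not applicable when not triggered.

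Report Aim 1 fidelity on the core only, with the number of applicable ratings for each item. Let all other items change as the pilot proceeds, date each version on the form, and report those changes as development output.

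This takes a few hours of drafting and needs no extra raters or recordings. The downside is that core items cannot be improved mid-pilot. A weakness found in one of them would be noted as a recommendation for the next trial.
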